#### eGFRcr

Female:	$Scr \leq 0.7 \text{ mg/dL}$	144 x $(Scr/0.7)^{-0.329}$ x 0.993 age
	Scr > 0.7 mg/dL	144 x $(Scr/0.7)^{-1.209}$ x 0.993 age
Male:	$Scr \leq 0.9 \text{ mg/dL}$	141 x (Scr/0.9) -0.411 x 0.993 age
	Scr > 0.9 mg/dL	141 x (Scr/0.9) -1.209 x 0.993 age
eGFRcyst		
	Scyst $\leq 0.8 \text{ mg/L}$	133 x $(Scyst/0,8)^{-0.499}$ x $0.996^{age}$ [x 0.932 if female]
	$S_{cyst} > 0.8 \text{ mg/L}$	133 x $(S_{cyst}/0,8)^{-1.328}$ x $0.996^{age}$ [x 0.932 if female]

Scr = serum creatinine (mg/dL), Scyst = serum cystatin C (mg/L)

Any subjects who have an eGFRcr (by Cockcroft-Gault) <50 mL/min, and who also experience >20% reduction in eGFRcyst (by CKD-EPI) from baseline, or who have other clinical and/or laboratory evidence of acute renal failure will be discussed with the sponsor's medical monitor and may permanently discontinue study drugs. For subjects with eGFRcr <50 mL/min who are not discontinued based on toxicity management procedures above and considered to have stable renal function per principal investigator and medical monitor, it is not mandatory to repeat eGFR assessments within 3 days.

All subjects with negative or trace proteinuria at baseline who develop >1+ proteinuria on urinalysis must have a urinalysis repeated, with a concurrent urine chemistry, within 2 weeks of receipt of results. Upon confirmation of proteinuria, subjects will be asked to return to the clinic for a scheduled or unscheduled FU visit. It is recommended that the investigator contact the sponsor's medical monitor to discuss if further consultation with a nephrologist is clinically warranted.

Once an individual subject has developed any of these renal changes and the above management guidelines have been applied, it is not necessary to further unscheduled repeat evaluations if it is determined that it is safe for the subject to continue on treatment with standard visits as described in the protocol.

For subjects who are randomized to the control arm, please refer to the local Prescribing Information of Truvada® with regard to dose adjustment or treatment discontinuation in case of renal impairment.

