2.5. Visit Windows

2.5.1. Trial Phases

Phases will be constructed for each subject as follows for adverse events, concomitant therapies, and for the determination of the worst-case/toxicity/change in the cross-tabulations.

Trial phase	Start date	End date
Screening	Minimum of Date of signing the informed consent and Date of the screening visit	1 day before start of treatment
Comparative Treatment Phase	Date of the first intake (after randomization)	
For initial D/C/F/TAF subjects, in order of priority:
 
 - Week 48 visit date; if missing then - Projected Week 48 visit date, where projected Week 48 visit date = baseline visit date + (7 *48) 
For late switchers: Date of first D/C/F/TAF intake-1 day
 
In case of withdrawal use:
 
 - Minimum(last intake date of study drug, study withdrawal date) + 2 days
Extended Treatment Phase (Extension)	Last Date of Comparative Treatment Phase +1 day	
 - Week 96 visit date; if missing then - Projected Week 96 visit date, where projected Week 96 visit date = baseline visit date + (7 *96) 
In case of withdrawal use:
 
 - Minimum (last intake date of study drug, study withdrawal date) + 2 days
Follow-up	End of last treatment phase +1 day	Trial termination date for all groups (date of last contact)

Data up to each subject's Week 96 visit are in scope for this analysis, DXA data (DP domain) up to Week 96 visit+28 days, and if applicable, any (confirmatory) viral load or genotype/phenotype results immediately subsequent to Week 96 (up to 6 weeks).

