5.5.3.2. Proximal renal tubular function

Proteinuria by Quantitative Assessment

Total urine protein, total urine albumin, urine protein to creatinine ratio (UPCR) and urine albumin to creatinine ratio (UACR) will be summarized by treatment arm and visit using descriptive statistics. The number and proportion of subjects with UACR and UPCR results in the following categories at Week 96 will be tabulates:

- UACR: < 30, 30 to 300, >300 mg/g
- UPCR: < 200 mg/g versus ≥ 200 mg/g

Median (Q1, Q3) percent change from reference over time will be plotted by treatment group.

The evolution over time of total urine protein and total urine albumin will also be presented.

Proteinuria by Urinalysis (Dipstick)

Treatment-emergent proteinuria by urinalysis (dipstick) through Week 96 will be summarized by treatment group. Cross-tabulation of grades at Week 96 versus reference will also be presented.

Other Renal Biomarkers

Selected renal biomarkers retinol binding protein (RBP) and beta-2-microglobulin, RBP to creatinine ratio and beta-2-microglobulin to creatinine ratio will be summarized by treatment arm and visit using descriptive statistics.

The proportions of subjects with beta-2-microglobulin to creatinine ratio ≤ 300 $\mu\text{g/g}$ and $>300\text{mg/g}$ will be tabulated.

The number and proportion of subjects with retinal binding protein to creatinine ratio results in the following categories at Week 96 will be tabulated:

- < 50 years of age (at the time of lab assessment): < 130 mcg/g creatinine, ≥ 130 mcg/g creatinine
- ≥ 50 years of age (at the time of lab assessment): < 172 mcg/g creatinine, ≥ 172 mcg/g creatinine

Phosphate excretion

Other renal biomarkers include urine fractional excretion of phosphate (FEPO4) that will be summarized by treatment arm and visit using descriptive statistics.

Urine fractional excretion of Phosphate (FEPO4) will be calculated as follows:

- Based on unadjusted serum creatinine:
$$\text{FEPO4 (\%)} = (\text{SCr} \times \text{UPO4}) / (\text{SPO4} \times \text{UCr}) \times 100 (\%)$$

The reference, post-reference, and change from reference in FEPO4 will be summarized by treatment arm and visit using descriptive statistics. Median (Q1, Q3) change from baseline in FEPO4 over time will be plotted by treatment group.

Subclinical renal proximal tubulopathy

Potential Markers of Renal Proximal Tubulopathy are

1. Increase in serum creatinine ≥ 0.40 mg/dL from reference.

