2. Confirmed ≥ 2 grade level increase from reference in graded proteinuria
3. Confirmed ≥ 1 grade level increase from reference in graded hypophosphatemia
4. Confirmed ≥ 1 grade level increase from reference in graded glycosuria concurrent with serum glucose ≤ 100 mg/dL (normoglycemic glycosuria)

A confirmed laboratory abnormality is defined as an abnormality observed at 2 consecutive post-reference measurements or an abnormality observed at 1 measurement followed by study drug discontinuation

A subclinical renal proximal tubulopathy is defined as confirmed abnormalities in any 2 out of the 4 renal parameters (serum creatinine and one or more of the 3 other markers of tubular dysfunction).

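### For subjects who continue D/C/F/TAF past Week 96, a tubulopathy marker first abnormal at the Week 96 visit cannot be confirmed by a repeat under the SAP's data cut

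*SAP*

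**What the plan says.** SAP 5.5.3.2 lists four markers: serum creatinine, proteinuria, hypophosphatemia and normoglycemic glycosuria. The composite is strict: "A subclinical renal proximal tubulopathy is defined as confirmed abnormalities in any 2 out of the 4 renal parameters", with creatinine as one of the two. Confirmation has two routes: "A confirmed laboratory abnormality is defined as an abnormality observed at 2 consecutive post-reference measurements or an abnormality observed at 1 measurement". The second, in full, is "an abnormality observed at 1 measurement followed by study drug discontinuation", which needs no second sample.

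SAP 2.5.1 sets the data cut at each subject's own visit: "Week 96 visit are in scope for this analysis, DXA data (DP domain) up to Week 96 visit+28 days". The only other allowance is for virology: "confirmatory) viral load or genotype/phenotype results immediately subsequent to Week 96 (up to 6 weeks". Renal laboratory tests are not mentioned.

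SAP 2.6.1 says that the safety analysis includes the data collected at the 30-day follow-up visit. It does not say how this fits with the cut in 2.5.1.

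Protocol 9.5.4 says that subjects with negative or trace baseline proteinuria who develop more than 1+ "must have a urinalysis repeated, with a concurrent urine chemistry, within 2 weeks of receipt of results". The same section calls for serum creatinine to be measured again when eGFRcr falls below 50 mL/min. Protocol 9.4.2 asks for a confirmatory test after a grade 3 or 4 laboratory abnormality.

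**The concern.** A rule that requires confirmation needs somewhere for the confirming value to come from. For a subject who remains on drug, the first route needs a later sample. If the marker first turns abnormal at the Week 96 visit, that sample falls outside the cut. The second route is closed as well, because the subject has not stopped treatment. The subject is then scored as having no event, even where a repeat was taken days later and was also abnormal.

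The SAP avoids this problem for viral load. It keeps retests for up to 6 weeks after Week 96, and SAP 4.6.1 also counts a last on-treatment value at or above the threshold at the cut-off. The renal rule has neither provision. At stake is the completeness of a renal safety count in a program where TAF's renal profile is of interest, and whether a reader can tell a true absence of events from a confirmation that was never possible.

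**Working it through.** The documents state no rate, sample size or power for this endpoint, so there is no planned figure to reproduce. The check sets the definition against the cut and then counts visits.

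**Step 1: can a first abnormality at Week 96 be confirmed?** Take a subject who attends Week 96 and continues D/C/F/TAF, as SAP 1.2 offers to all subjects.

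- Route 1 (two consecutive measurements): the next scheduled visit is 6 months later (SAP 1.2) and outside the cut. An unscheduled repeat after the visit is also outside it. Route 1 is closed.
- Route 2 (one measurement, then discontinuation): the subject has not discontinued. A later discontinuation falls outside the cut, and the SAP does not say whether stopping exactly at Week 96 counts. Route 2 does not apply to a continuer.

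**Step 2: the composite widens the gap slightly.** Two confirmed markers are needed, one of them creatinine. A subject whose creatinine increase is already confirmed, but whose second marker first appears at Week 96, is also scored as no event. The list entry for creatinine ("Increase in serum creatinine" of at least 0.40 mg/dL) lacks the word 'confirmed' that the other three entries carry, while the composite asks for confirmed abnormalities. The SAP should make these agree.

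**Step 3: does the protocol generate repeats that the cut discards?** For proteinuria, yes. The protocol's DAIDS table grades 1+ as grade 1 and 2+ as grade 2. From a grade 0 reference, the SAP's increase of at least 2 grades therefore begins at 2+, which is also the first dipstick level above the protocol's 1+ trigger. If the Week 96 sample is the trigger, the repeat necessarily comes after the visit. Creatinine repeats are called for only when eGFRcr is below 50 mL/min, and other repeats only for grade 3 or 4 values. Protocol 9.5 also words its guidelines as strongly recommended in the extension phase, so repeats will exist for some subjects and markers, not all.

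**Step 4: how much of follow-up is affected?** Scheduled chemistry and urinalysis visits come from the Time and Events Schedule. The reference for late switchers is the last value before the switch (SAP 2.9), with the switch at Week 52.

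| Display (SAP section 5) | Scheduled visits | Share of visits lost | Share of time lost |
|---|---|---|---|
| Initial switchers, baseline to Week 96 | 2, 4, 8, 12, 24, 36, 48, 60, 72, 84, 96 (11) | 1/11 = 9.1% | (96 − 84)/96 = 12/96 = 12.5% |
| Initial switchers, extension | 60, 72, 84, 96 (4) | 1/4 = 25% | 12/(96 − 48) = 12/48 = 25% |
| Late switchers, extension | 60, 72, 84, 96 (4) | 1/4 = 25% | 12/(96 − 52) = 12/44 = 27.3% |

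The time shares assume uniform onset, scheduled visits only, and subjects who continue treatment. They are shares of the opportunity for onset, not observed or expected losses of events.

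**The case against.** The strongest case against is that little depends on this. SAP 1.3 tests no hypothesis at Week 96, and the endpoint is descriptive. Single abnormal values at Week 96 remain visible elsewhere: in worst-grade cross-tabulations and abnormal-value listings (SAP 5.5.2), in GFR stage tables (5.5.3.1), and in the dipstick, UPCR and UACR summaries (5.5.3.2). A separate SAP will cover the final analysis. Any confirmation rule loses something at a data cut, and the SAP accepts this for viral blips, which are classified only up to the lower limit of the Week 96 window (4.6.1). All of this stands and keeps the point small. It does not show how the composite treats these subjects, which the SAP leaves unstated.

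A fair objection to the remedy is that the proteinuria repeat consists of urinalysis and urine chemistry, without serum creatinine, so a longer cut would not always supply both components. That also stands, and is why a separate row for unconfirmed values is needed.

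The 30-day follow-up text in SAP 2.6.1 might seem to close the gap. It rarely would. Protocol 9.1.5.2 requires that visit only for subjects with an ongoing AE or SAE at their last study visit. For continuers Week 96 is not the last visit, and Protocol 12.2 says that laboratory abnormalities are usually not recorded as AEs.

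A reader might also infer three stronger things that the documents do not support:

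- That an abnormality at Week 96 can never be scored. The discontinuation route needs no second sample, and the Week 96 window runs from Day 631 to Day 714, so an abnormal sample in that window followed by discontinuation qualifies. An unscheduled abnormal sample shortly before the Week 96 visit could also complete a consecutive pair.
- That the loss is inherently unequal between groups (9% against 25% of visits). That contrast arises only when 96 weeks in one group are set beside 44 in the other. In the extension display both groups have the same four visits.
- That a central TAF comparison is distorted. In the extension both groups take D/C/F/TAF, and the renal comparisons planned at Week 96 are within arm against reference.

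**Conclusion.** The gap is real and narrow. For subjects who attend Week 96 and stay on D/C/F/TAF, a marker first abnormal at that visit cannot be confirmed by a repeat, because SAP 2.5.1 gives renal laboratory tests no allowance after Week 96. The effect is a modest undercount of a descriptive endpoint, always towards fewer events. The last visit of each display cannot start a confirmed abnormality, and Step 4 gives the shares. The number of events lost cannot be estimated, because the documents give neither an event rate nor an onset pattern. No hypothesis test or primary conclusion is affected. This is a cheap improvement with a small gain.

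**What to change.** 1. In SAP 2.5.1, extend the allowance after Week 96 to repeat renal laboratory tests (serum creatinine, phosphate and glucose, urinalysis and urine chemistry) already collected within 6 weeks after the Week 96 visit, and state that they may confirm an abnormality first seen at that visit.
2. In the tubulopathy table, add a separate row, 'unconfirmed at cut-off', for markers first abnormal at Week 96 with no repeat. Not every marker has a mandated repeat, so the first change alone would leave some subjects unaccounted for.
3. Reconcile the 2.5.1 cut with the 30-day follow-up wording in 2.6.1. In 5.5.3.2, state whether stopping drug at Week 96 counts as discontinuation and whether creatinine must be confirmed.

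The cost is a few clauses, one table row and a slightly later cut for these tests. No new samples or visits are needed.

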5.6. Vital Signs and Physical Examination Findings

5.6.1. Definitions

The following vital signs parameters will be analyzed:

- pulse (bpm)
- systolic blood pressure, SBP (mmHg)
- diastolic blood pressure, DBP (mmHg)
- weight (kg)

Pulse, DBP and SBP are classified in the following abnormality codes:

	Pulse (bpm)	DBP (mmHg)	SBP (mmHg)
Abnormally low	≤ 50	≤ 50	≤ 90
Grade 1 or mild	-	> 90 - < 100	> 140 - < 160
Grade 2 or moderate	-	≥ 100 - < 110	≥ 160 - < 180
Grade 3 or severe	-	≥ 110	≥ 180
Abnormally high	≥ 120	-	-

In determining abnormalities, the following rules are applied:

- worst grades/abnormalities are determined over the whole observational period for each trial phase separately, including post-reference scheduled *and* unscheduled measurements of that phase.
- The abnormalities ‘abnormally low’ and ‘abnormally high’/grades are considered equally important, i.e. if a subject has as well an abnormally low as an abnormally high or graded value post-reference, both abnormalities are shown in the tables. (This means that the sum of the percentages can be more than 100%).

Definition treatment-emergent:

An abnormality will be considered treatment-emergent in a particular phase if it is worse than the reference corresponding to this phase. If the reference is missing, the abnormality is always considered as treatment-emergent. A shift from ‘abnormally low’ at reference to ‘abnormally high’ or ‘grade ...’ post reference (or vice versa) is also treatment-emergent.

5.6.2. Analysis methods

Descriptive statistics for the actual values and changes from reference per timepoint will be presented. For weight, comparative treatment phase and extended treatment phase will be presented for Initial switch group as well as Late switch group.

Cross-tabulations for the worst abnormalities versus reference per vital signs test will be produced.

Abnormal physical examination (symptom-directed) findings will be listed.

5.7. Bone Investigations

5.7.1. Definitions

Bone formation markers:

- Serum total alkaline phosphatase (ALP)
- Serum type 1 procollagen N-terminal (PINP)

Bone resorption markers:

- Urinary or serum collagen type 1 cross-linked C-telopeptide (CTX)

Other:

- parathyroid hormone (PTH)
- 25-hydroxy vitamin D (25-OH VitD)

Bone mineral density (BMD)

DXA scan of spine and hip (data of other regions, e.g. femoral neck may also be analyzed if available):

- BMD values
- BMD T- and Z-scores

The BMD status will be derived based on T-scores using the following categories:

	Osteoporosis	Osteopenia	Normal
T-score	< -2.5	-2.5 to < -1	≥ -1

5.7.2. Analysis methods

Bone Biomarkers:

Descriptive statistics for the actual values, changes and percent changes from reference per time point will be presented for each bone biomarker.

DXA scan:

Descriptive statistics for the actual values, change and percent changes from reference per time point will be presented for BMD parameters (including T- and Z-scores).

Within-treatment arm comparison versus reference at Week 96 will be assessed using Wilcoxon signed-rank test. The proportions of subjects with at least 3% change (decrease and increase separately) from reference in BMD will be presented at Week 96. Percent change from reference will also be tabulated based on thresholds; 5% and 7%.

BMD status will be tabulated (n, %) separately per time point, based on the T-score categories. Cross-tabulations for the BMD status at Week 96 versus reference will be produced.

REFERENCES

1. Guidance for Industry. Antiretroviral Drugs Using Plasma HIV RNA Measurements Clinical Considerations for Accelerated and Traditional Approval. October 2002.

ATTACHMENTS

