# 11.1.2. Secondary Endpoints

Secondary endpoints in this study are:

- The proportion of subjects having confirmed virologic rebound through 24 and 96 weeks of treatment;
- The time to virologic rebound in weeks;
- The proportion of subjects experiencing grade 3 and 4 AEs through 24, 48, and 96 weeks of treatment;
- The proportion of subjects experiencing SAEs and premature discontinuations due to AEs through 24, 48, and 96 weeks of treatment;
- The change from baseline in serum creatinine, eGFRcr (by Cockcroft-Gault and by CKD-EPI) and eGFRcyst (by CKD-EPI) at Weeks 24, 48, and 96;
- The change from baseline in renal biomarkers at Weeks 24, 48, and 96;

- Clinical Protocol TMC114IFD3013 Amendment 4
- The proportion of subjects with HIV-1 RNA <20, <50, and <200 copies/mL at Weeks 24, 48, and 96 as defined by the FDA snapshot analysis and TLOVR algorithm;
- The change from baseline in CD4+ cell count at Weeks 24, 48, and 96;
- Adherence to drug intake based on drug accountability through 24, 48, and 96 weeks;
- Genotypic, and phenotypic if applicable, resistance to ARVs in the 2 treatment arms in subjects with confirmed HIV-1 RNA rebound through Weeks 24, 48, and 96;
- Pharmacokinetic parameters for DRV in the D/C/F/TAF arm.

Secondary endpoints to be assessed in subjects participating in a bone investigation substudy at selected study sites:

- The percent change from baseline in bone biomarkers CTX, P1NP, PTH, and 25-hydroxy vitamin D at Weeks 24, 48, and 96.
- The percent change from baseline in spine and hip BMD and change from baseline in BMD T-score at Weeks 24, 48, and 96.

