#### **Bone investigations**

Baseline, post-baseline, and the percent change from baseline at Weeks 24, 48, and 96 for selected bone biomarkers, including CTX, P1NP, PTH, and 25-hydroxy vitamin D, will be summarized by treatment arm and visit using descriptive statistics. The within-treatment comparison will be done using Wilcoxon signed-rank test. The comparison between the 2 treatment arms will be performed using the Van Elteren test stratified for bPI used at screening.

The percent change from baseline at Weeks 24, 48, and 96 in spine and hip BMD as well as the change from baseline in BMD T-score will be summarized by treatment arm and visit using descriptive statistics. The between-treatment differences at Weeks 24 and 48 will be estimated using ANCOVA model, including baseline BMD value and other clinically relevant factors (if deemed necessary) in the model. The within-treatment comparison will be done using paired t-test. A supportive longitudinal repeated measures analysis will be performed on this endpoint to obtain an estimate of the between-treatment difference along with its 95% CI at Weeks 24 and 48. This model will include post-baseline percent change from baseline as a response variable, terms for treatment, visit, the interaction of visit and treatment and the corresponding baseline BMD value as a covariate and other clinically relevant factors (if deemed necessary). An unstructured covariance matrix will be used to model the correlation among repeated measurements.

The BMD T-score will be summarized descriptively. BMD status based on the T-score (normal:  $\geq$ -1; osteopenia: from <-1 to -2.5; osteoporosis: <-2.5) will be tabulated.

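### SAP 5.7.2 adds percent change from reference for BMD T- and Z-scores, signed scales on which that statistic reverses direction below zero and fails at zero

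*SAP*

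**What the plan says.** SAP 5.7.2, under DXA scan, asks for descriptive statistics of the observed values and adds that "change and percent changes from reference per time point will be presented for BMD parameters (including T- and Z-scores". The parenthesis names the scores, so they are included on purpose. SAP 5.7.1 lists "BMD T- and Z-scores" among the DXA variables and continues: "The BMD status will be derived based on T-scores using the following categories". The bands are below -2.5, -2.5 to below -1, and -1 or above. The SAP gives no formula for percent change, no rule for a negative or zero reference, and no exemption for the scores.

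The protocol keeps the two measures apart. Its secondary endpoint in 11.1.2 is "The percent change from baseline in spine and hip BMD and change from baseline in BMD T-score at Weeks 24, 48, and 96". Protocol 11.6, Bone investigations, repeats the pairing: percent change for BMD, then "change from baseline in BMD T-score will be summarized by treatment arm and visit using descriptive statistics". The Synopsis does the same, as do the substudy objectives restated in SAP 1.1. Z-score is not a protocol endpoint. In the protocol it appears only in the DAIDS grading table (Attachment 2).

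SAP 5.7.2 then sets thresholds. The first is tied to BMD: "The proportions of subjects with at least 3% change (decrease and increase separately) from reference in BMD will be presented at Week 96". The next names no variable: "Percent change from reference will also be tabulated based on thresholds; 5% and 7" (the last figure is 7%).

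**The concern.** Percent change is meaningful on a ratio scale such as BMD in absolute units. A T- or Z-score is a standardised difference. Its zero marks the reference-population mean, not an absence of bone, and the SAP's own *Normal* band includes zero. Dividing a change by such a reference gives a figure whose sign and size depend on where the subject started as much as on what happened.

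What is at stake is readability. A T-score percent table would stand beside a BMD percent table from the same scans and point the opposite way for every subject whose reference score is negative. All subjects in the osteopenia and osteoporosis bands have a negative T-score, and they are the ones of most interest for bone safety.

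**Working it through.** **1. The plan's own bone figure.** SAP 1.4 and Protocol 11.2 state about 98% power for a 2% difference in percent change in spine BMD, with SD 4% and 200 versus 100 subjects. No alpha is stated for the substudy, so two-sided 0.05 is assumed.

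- SE = 4 × √(1/200 + 1/100) = 0.490
- 2 / 0.490 = 4.08, and 4.08 − 1.96 = 2.12
- Φ(2.12) = 0.983 (0.982 with the noncentral t)

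The stated figure is reproduced. It concerns BMD percent change, so this point does not affect it.

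**2. Percent change on a signed score.** The usual formula is 100 × (post − reference) / reference.

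| Reference to post | Plain change | Percent change |
|---|---|---|
| -2.6 to -2.4 | +0.2 | -7.7% |
| -2.0 to -1.8 | +0.2 | -10% |
| -1.0 to -0.8 | +0.2 | -20% |
| -0.5 to -0.3 | +0.2 | -40% |
| -0.1 to +0.1 | +0.2 | -200% |
| +1.0 to +1.2 | +0.2 | +20% |
| +1.0 to +0.8 | -0.2 | -20% |
| +0.1 to -0.1 | -0.2 | -200% |
| 0.0 to any value | any | undefined |

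One and the same gain of 0.2 ranges from -200% to +20%. A gain from -1.0 and a loss from +1.0 give the same number. With |reference| as divisor the gains become positive, but the gain from -0.1 is still 200% and a reference of 0 is still undefined.

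**3. How many subjects.** The documents give no distribution of reference scores. Assumptions: reference T-score normal with mean m and SD 1.1, scores recorded to one decimal, and true change with mean +0.15 and SD 0.3. Simulated results, with expected counts scaled to 300 substudy subjects, per score and site:

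| m | Gains shown as falls | Mean percent change | SD of percent change | Expected undefined of 300 |
|---|---|---|---|---|
| -1.5 | 92% | -10.3 | 73 | 4.3 |
| -1.0 | 83% | -9.4 | 94 | 7.2 |
| -0.5 | 68% | -5.8 | 109 | 9.8 |
| 0 | 50% | -0.2 | 115 | 10.9 |
| +0.5 | 32% | +5.7 | 109 | 9.8 |

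The true mean change is +0.15 in every row. The row for m = -1.0 can be checked by hand:

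- negative as recorded: Φ((-0.05 + 1.0)/1.1) = Φ(0.864) = 0.806
- recorded as 0.0: Φ(1.05/1.1) − Φ(0.95/1.1) = 0.024, and 0.024 × 300 = 7.2
- share of gains shown as falls, among defined values: 0.806 / (1 − 0.024) = 0.83

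**4. After the change.** With plain change, every gain of 0.2 is reported as +0.2 whatever the reference, and nothing is undefined.

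**The case against.** The strongest reply is that nothing is lost. The same SAP sentence still delivers plain change in T-score, which is the protocol's measure, so the SAP adds a column and replaces nothing. That stands. A reader might infer that the SAP has abandoned the protocol endpoint, but it has not.

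A reader might also infer that the percentages would point the wrong way for most subjects. The documents do not support this. The T-score bands are classification cut-offs, not a distribution, and the *Normal* band holds zero and all positive values. In the table above the share falls to 50% at a mean of 0 and 32% at +0.5. The situation for Z-scores is even less certain.

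Undefined values need a reference of exactly 0, and recording precision is not stated. They are likely with one decimal and rare with more. Since the SAP gives no formula, a programmer might also divide by the absolute reference. That would cure the sign but not the inflation or the zero.

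Nor do the documents support reading this as a threat to the bone conclusions. This is the Week 96 SAP, with no formal hypothesis (SAP 1.3) and descriptive reporting. The protocol's between-arm BMD estimates are at Weeks 24 and 48. The 3% table is already defined on BMD. The 5% and 7% figures match the spine and hip BMD decreases in Protocol 9.5.5, so BMD is clearly the intended variable even though the sentence omits it.

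What survives is that the SAP expressly orders a statistic that misleads for any negative reference.

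**Conclusion.** The point holds as a minor drafting defect. As written, SAP 5.7.2 calls for a summary that, with the usual formula, reverses direction for every negative reference score, inflates values near zero and is undefined at zero. This follows from arithmetic and the signed scale alone; one negative reference is enough.

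The extent is conditional. About 32% to 92% of gains would be shown as falls for assumed mean reference scores of +0.5 to -1.5, with about 4 to 11 undefined values per 300 if scores carry one decimal. These figures rest on the assumed SDs, mean gain and rounding, none of which is in the documents.

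The affected output is one descriptive secondary summary. Plain change in the scores, BMD percent change, BMD status shifts, the 98% substudy power and the primary endpoint are all unaffected.

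**What to change.** In SAP 5.7.2:

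- Limit percent change from reference to BMD in absolute units.
- Present T-scores as observed values and absolute change only, as Protocol 11.1.2 and 11.6 specify. Treat Z-scores likewise, for the same reason; the protocol itself is silent on them.
- Add the words *in BMD* to the sentence on the 5% and 7% thresholds, consistent with Protocol 9.5.5. The 3% sentence needs no change.

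The cost is an edit to two SAP sentences and fewer outputs to program. No valid information is lost.
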